## 5 STUDY DESIGN

# 5.1 Overall Study Design and Plan

This is a randomized, open-label, Phase 2/3 study of CO-1686 versus erlotinib as a first-line treatment for patients with advanced/metastatic NSCLC whose tumors have EGFR-activating mutations. The study will consist of Phase 2 and Phase 3 parts which will use the same enrollment criteria and treatment assignment principles. The Phase 2 part is an open-label study; in the Phase 3 part, the sponsor will be blinded to efficacy and safety results aggregated by randomized treatment group. The Phase 2 part will enroll approximately 200 patients. Data from the Phase 2 part will be used to inform on the sample size in the Phase 3 part of the study. The sample size of the Phase 3 component will be capped at approximately 1,000 patients. The Phase 3 part will include up to 3 interim analyses. At each interim analysis, enrollment into the Phase 3 part may be stopped if there is a high probability of success in the Phase 3 part of the study. If enrollment is stopped early, the Phase 3 part of the study will continue until at least 70% of the randomized patients have a PFS event.

Patients will be stratified for randomization according to the followings factors:

- Sensitizing EGFR mutation (L858R, del19, or other)
- Territory of residence at time of randomization (Asia or non-Asia)

Patients will be randomized in a 1:1 ratio to Treatment Arm #1 or #2:

- Treatment Arm #1 CO-1686, 500 mg orally (PO), with food, BID
- Treatment Arm #2 erlotinib, 150 mg PO, on an empty stomach, once daily (QD)

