#### 11.2 Statistical Methods

#### 11.2.1 General Considerations

Quantitative variables will be summarized using descriptive statistics (N, mean, standard deviation, median, minimum, and maximum) and/or frequency and percentages for medically relevant categories. Categorical variables will be presented using frequencies and percentages.

Kaplan-Meier methodology will be used to summarize time-to-event variables. The number of patients with events and the number of censored patients will also be presented. The stratified logrank test will be used to compare the time-to-event distributions between the randomized treatment groups. The same variables used to stratify the randomization will be used in the stratified analyses. In addition, the Cox proportional hazards model will be used to estimate the HR between the randomized treatment groups.

The Fisher's Exact Test will be used to compare frequencies between treatment groups and the t-test will be used for comparing means between treatment groups.

All data will be used to their maximum possible extent but without any imputations for missing data. Results from Phase 2 and Phase 3 will be presented separately and pooled.

All statistical analyses will be conducted with the statistical analysis software (SAS®) system, Version 9.1 or higher.

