Analyses of changes and/or percent changes from baseline will be analyzed for each scheduled post-baseline visit and for the final visit for the EQ-5D instrument and the EQ-VAS. If more than one measurement exists for a patient on a particular day, then an arithmetic average will be calculated. This average will be considered to be that patient's measurement for that day. Post-baseline measurements more than 28 days after the last dose of protocol-specified treatment will not be included. Patients that do not have both a baseline measurement and at least one post-baseline measurement will not be included.

At a given visit, the change and/or percent change from baseline will be compared between the randomized treatment groups using an analysis of covariance (ANCOVA), using the treatment as a categorical factor and baseline measurement for the parameter as a continuous covariate.

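### The EQ-5D ANCOVA leaves out the randomisation strata and lets percent change be tested beside change from baseline; both can be tightened at almost no cost.

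*Combined protocol and SAP*

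**What the plan says.** All references are to the combined protocol and SAP.

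- **Outcome compared.** Section 11.2.4.2 (Patient Reported Outcomes) says: "At a given visit, the change and/or percent change from baseline will be compared between the randomized treatment groups". Just before that, it says that changes and/or percent changes "will be analyzed for each scheduled post-baseline visit and for the final visit for the EQ-5D instrument and the EQ-VAS".
- **Model.** The comparison is an ANCOVA, "using the treatment as a categorical factor and baseline measurement for the parameter as a continuous covariate". No other term is listed.
- **Endpoint.** The Synopsis and Section 4.2.2 define the secondary quality-of-life endpoint as change from baseline. Neither list mentions percent change.
- **Randomisation.** Sections 5.1 and 7.2 stratify by sensitizing EGFR mutation (L858R, del19 or other) and by territory (Asia or non-Asia), which makes 3 × 2 = 6 cells.
- **General rules.** Section 11.2.1 says "The same variables used to stratify the randomization will be used in the stratified analyses", directly after it introduces the stratified logrank test. Its default for means is that "the t-test will be used for comparing means between treatment groups".
- **Primary analysis.** Section 11.2.4.1 stratifies the PFS analysis by both factors and combines the exon 19 deletion and other-mutation groups if either has fewer than 30 patients.

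**The concern.** Two features of the EQ-5D analysis are looser than they need to be.

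First, when allocation is stratified on factors that predict the outcome, a model without those factors counts between-stratum variation as noise. Its standard error is then larger than the design warrants. Both factors are already recorded for every patient, so any such loss is avoidable.

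Second, the and/or wording allows absolute change, percent change or both to be the tested quantity. The endpoint lists point to absolute change, but nothing in the analysis section says that they govern. That leaves room to choose between two tests once results are visible. Percent change is also a poor scale for this purpose: it cannot be computed from a zero baseline, it grows without limit as the baseline approaches zero, and it does not fit well with a linear adjustment for baseline.

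At stake are some precision and the clarity of a secondary patient-reported comparison.

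**Working it through.** **The plan's own figure.** The documents give no power, SD or effect size for the EQ-5D. The only power statement (Section 11.3) is for PFS: 640 events, about 80% power, HR 0.80, one-sided 0.025. It reproduces:

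- Schoenfeld: 4 × (1.960 + 0.842)² / (ln 0.80)² = 631 events.
- Freedman: (1.80/0.20)² × (1.960 + 0.842)² = 636 events.
- Power at 640 events: 80.6%.

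The point below does not depend on this figure.

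**Omitted strata.** Let R² be the share of outcome variance that the strata explain after baseline. The documents do not give it, so 0 to 0.10 is assumed. Set power at 80% (two-sided 0.05) for the model with strata, so the standardised effect is 1.960 + 0.842 = 2.802.

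- Standard error ratio, without strata to with strata: 1/√(1 − R²).
- Power if the whole inflation is charged to the analysis: Φ(2.802 × √(1 − R²) − 1.960).
- Effective size of 500 per arm (the Phase 3 maximum, Section 6.1): 500 × (1 − R²).

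| R² | SE ratio | Power without strata | 500 per arm is worth |
|---|---|---|---|
| 0 | 1.000 | 80.0% | 500 |
| 0.01 | 1.005 | 79.6% | 495 |
| 0.02 | 1.010 | 79.2% | 490 |
| 0.05 | 1.026 | 78.0% | 475 |
| 0.10 | 1.054 | 75.7% | 450 |

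These power figures are a lower limit. Stratified allocation already balances the strata, so the estimate itself is no noisier; only its reported standard error is too large. On that basis power is Φ(2.802 − 1.960/√(1 − R²)), which is 78.5% at R² = 0.05 and 76.9% at R² = 0.10. True type I error is 2 × [1 − Φ(1.960/√(1 − R²))], which is 4.4% and 3.9%. The error is on the conservative side.

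**Simulation of both parts.** There were 4,000 trials per setting, with 100 per arm (the Phase 2 size), six strata, permuted blocks of 4 and two-sided 0.05. Scores ran from 0 to 100, with baseline mean 65, SD 20 and correlation 0.5; the treatment effect was 0 or 0.35 SD (7 points). Baselines were held at 5 or above, so the zero-baseline problem is not in these results. All settings are assumptions.

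| R² | Type I: change | Type I: either outcome | Power: change | Power: percent change | Power: change, with strata |
|---|---|---|---|---|---|
| 0 | 4.9% | 6.8% | 79.2% | 55.5% | 79.4% |
| 0.05 | 5.0% | 7.3% | 80.6% | 55.7% | 82.0% |
| 0.10 | 3.6% | 5.6% | 82.3% | 54.6% | 84.3% |

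Monte Carlo error is about 0.3 points near 5% (√(0.05 × 0.95/4000)) and about 0.6 points near 80% (√(0.80 × 0.20/4000)).

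**Number of tests.** Questionnaires are due at Cycles 3, 5 and 7 and later (Section 9.6.5). Counting only those three visits plus the final visit, for two scores, gives 4 × 2 = 8 comparisons with one outcome and 16 with two.

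**Scale.** The same 5-point gain is (10 − 5)/5 = 100% from a baseline of 5 and (55 − 50)/50 = 10% from a baseline of 50. This only illustrates the arithmetic: Section 11.2.4.2 gives a 0 to 100 range for the EORTC scales and no range for the EQ-5D or EQ-VAS.

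**The case against.** A baseline-adjusted ANCOVA in a 1:1 randomised trial is valid without the strata. The loss arises only if mutation type or territory predicts the outcome once baseline is in the model, and a territorial difference in the level of self-rated health would largely be absorbed by baseline. The documents contain no evidence either way. All of this stands, and it is why the range starts at zero.

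A reader might infer that the omission biases the comparison, inflates false positives or breaks the rule in Section 11.2.1. The documents do not support this. The rule covers the stratified analyses and follows the logrank sentence, and the same section's default for means is an unadjusted t-test. The ANCOVA therefore contradicts nothing, and it already goes beyond that default by adjusting for baseline.

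A reader might also infer that the endpoint is undefined. It is not: the Synopsis and Section 4.2.2 both name change from baseline. What remains is that Section 11.2.4.2 permits a second tested quantity that those lists do not contain.

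Finally, no alpha control or confirmatory claim attaches to these tests, which are already repeated at every visit. Development has been discontinued, no more patients will be enrolled, and the Extension Phase schedule (Appendix D, Table 4) lists no questionnaires. This lowers the importance, but it does not settle how data already collected are to be compared.

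**Conclusion.** The point holds as a minor improvement to a secondary patient-reported analysis.

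- **Strata.** There is no bias and no type I inflation. For an assumed R² of 0 to 0.10, the standard error is 0 to about 5% larger than needed and power is at most about 4 points lower. Once the balancing effect of stratified allocation is counted, the loss is nearer 3 points at R² = 0.10 (80.0% against 76.9%). It is nil if the strata do not predict the outcome, and the documents do not allow it to be sized further.
- **Percent change.** This is the stronger part. It adds a second candidate test for each visit and score, on a scale that fails at a zero baseline. Under the assumed settings it had power of about 55%, against about 79 to 82% for absolute change. Allowing either to count gave a type I error of 5.6 to 7.3% for one score at one visit.

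The primary PFS analysis is unaffected.

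**What to change.** In the EQ-5D part of Section 11.2.4.2:

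1. Name absolute change from baseline as the only outcome compared between arms, to match Section 4.2.2. Keep percent change as a descriptive summary at most.
2. Add EGFR mutation type and territory, as randomised, as factors in the ANCOVA beside treatment and baseline.
3. State a pooling rule for sparse mutation categories. The rule in Section 11.2.4.1 can be carried over, but it is written for PFS only and must be extended expressly. It matters most for the other-mutation group at late visits in Phase 2, with about 100 patients per arm at the start.

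The cost is a wording change and one extra line in the model. No new data are needed, because both factors are already collected for randomisation.

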#### **OVERALL SURVIVAL**

OS will be calculated as 1+ the number of days from the first dose of study drug to death due to any cause. Patients without a documented date of death will be censored on the date the patient was last known to be alive.

Kaplan-Meier methodology will be used to summarize OS and the treatment groups will be compared using the logrank test.

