## 11 STATISTICAL METHODS

## 11.1 Analysis Populations

The following analysis populations are defined for the study:

**Intent-to-treat (ITT) population**—all randomized patients; the primary efficacy analysis of the Phase 3 part will be performed using the ITT population.

**Tumor evaluable population**—all patients who received at least 1 dose of first-line CO-1686 or erlotinib, have measureable tumor lesions at baseline, and have at least 1 post-baseline tumor assessment.

**Safety population**—all patients who have received at least 1 dose of CO-1686 or erlotinib.

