#### 11.2.4.1 Primary Endpoint

The primary endpoint of the study is invPFS.

invPFS will be calculated as 1+ the number of days from the date of randomization to disease progression, as determined by the investigator or death due to any cause, whichever occurs first. Patients without a documented event of progression will be censored on the date of their last adequate tumor assessment (i.e., radiologic assessment) or date of randomization if no tumor assessments have been performed.

Kaplan-Meier methodology will be used to summarize invPFS. The stratified logrank and the HR will be used for comparing the invPFS distributions among the CO-1686 and erlotinib-treated patients. The invPFS analysis will be stratified by EGFR mutation status (L858R, exon 19 deletion, or other) and territory of residence at time of randomization (Asia vs non-Asia). If the exon 19 deletion subgroup or other mutation subgroup has fewer than 30 patients than these subgroups will be combined for this analysis.

A PFS sensitivity analysis based on an independent radiographic review (irrPFS) will be performed. The irrPFS is defined as the time from randomization to disease progression according to RECIST v1.1 as assessed by independent radiographic review, or death due to any cause, whichever occurs first.

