## PATIENT REPORTED OUTCOMES (QUALITY OF LIFE)

QOL will be measured using the PROs of EORTC QLQ-C30, EORTC QLQ-LC13, the DLQI, and the EQ-5D. 15-17

The EORTC questionnaires will be scored using the published scoring algorithms provided by the EORTC. For each item or scale, a linear transformation will be applied to standardize the raw score to a range from 0 to 100. A high scale score represents a higher response level.

Thus a **high score for a functional scale** represents a *high / healthy level of functioning*, a **high score for the global health status / QOL** represents a *high QOL*, but a **high score for a symptom scale / item** represents a *high level of symptomatology / problems*.

The baseline PRO measurement will be defined as the last value prior to or on the day of the first dose of CO-1686 or erlotinib. The on-treatment period will be defined as the day after the first dose of CO-1686 or erlotinib to 28 days after the last dose of protocol-specified treatment. QOL measurements collected during the on-treatment period will be included in the summary tables.

The summary of PRO data will include descriptive statistics (N, mean, standard deviation, minimum, median, and maximum) of the observed measurements at each visit during the on-treatment period. Summaries using descriptive statistics of the change or percent change from baseline to each visit during the on-treatment period may also be provided. Graphical presentations may be used to present the mean changes over time.

The time to a worsening in symptoms will be computed as 1+ the number of days from the date of randomization to the first instance of  $a \ge 10$  point increase from baseline in symptoms. Patients without an event will be censored on the date of their last assessment. Kaplan-Meier methodology will be used to summarize the time deterioration and the treatment groups will be compared using the logrank test and hazard ratio.

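### OS is timed from first dose and PFS from randomisation, so a randomised patient who is never dosed has no OS time; the OS origin and population should be corrected (minor)

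*Combined protocol and SAP*

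**What the plan says.** In the combined protocol and SAP, the Overall Survival paragraph of Section 11.2.4.2 reads: "OS will be calculated as 1+ the number of days from the first dose of study drug to death due to any cause". Where no death is recorded, the patient is censored when last known alive. The paragraph names no analysis population and has no rule for a patient without a first dose.

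Section 11.2.4.1 uses a different origin for the primary endpoint: "invPFS will be calculated as 1+ the number of days from the date of randomization to disease progression". The independently reviewed version matches it: "The irrPFS is defined as the time from randomization to disease progression according to RECIST v1.1 as assessed by independent radiographic review". A patient with no scans still receives a PFS time, because censoring falls back to the last tumour assessment "or date of randomization if no tumor assessments have been performed".

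Section 11.1 separates randomised from dosed patients. ITT is "all randomized patients; the primary efficacy analysis of the Phase 3 part will be performed using the ITT population". The safety population is "all patients who have received at least 1 dose of CO-1686 or erlotinib".

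Section 11.2.1 sets the general rule: "The stratified logrank test will be used to compare the time-to-event distributions between the randomized treatment groups". The same section says that missing data will not be imputed.

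**The concern.** Timing OS from first dose conditions the analysis on something that happens after randomisation. A patient who is randomised and never starts treatment has no start date, and none may be imputed, so that patient falls out of the OS comparison while remaining in the PFS comparison.

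The trial is open-label. Investigators and patients know the assigned drug, and only the sponsor is blinded, in Phase 3, to results aggregated by arm. Whether a patient starts treatment could therefore depend on the arm. If it did, and if non-starters had a different prognosis, an OS comparison restricted to starters would no longer compare the groups as randomised. Comparing OS between arms is a stated secondary objective in Section 4.1.2.

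**Working it through.** **1. Origins side by side**

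| Endpoint | Clock starts | Never-dosed patient |
|---|---|---|
| invPFS (11.2.4.1) | randomisation | has a time, by fallback if there are no scans |
| irrPFS (11.2.4.1) | randomisation | has a start date |
| OS (11.2.4.2) | first dose | no start date and no fallback |

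The plan gives no power or event count for OS, so there is no stated OS figure to reproduce. The 640-event calculation in Section 11.3 concerns PFS and is not affected.

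**2. Patients dosed on schedule.** The Synopsis and Sections 7.2 and 9.1 require the first dose within 3 days of randomisation and allow it on the same day. The change of origin therefore adds 0 to 3 days. The documents do not bound late starts. Take an extreme case in which one whole arm starts on day 3 and the other on day 0. Assume (none of this is from the documents) exponential survival with median OS 24 months, uniform accrual over 18 months and analysis at 36 months.

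- Death rate λ = ln 2 / 24 = 0.0289 per month.
- Follow-up runs uniformly from 18 to 36 months, so the mean of exp(−λC) is (0.595 − 0.354) / (0.0289 × 18) = 0.464.
- Mean observed time = (1 − 0.464) / 0.0289 = 18.6 months, or about 565 days.
- Adding 3 event-free days gives HR ≈ 1 / (1 + 3/565) = 0.995, or 1.005 with the arms reversed.

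**3. Number of never-dosed patients.** The documents give no rate. Assuming 0.5% to 5%:

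- Phase 3, planned maximum 1,000: 0.005 × 1,000 = 5 to 0.05 × 1,000 = 50.
- Phase 2, planned 200: 0.005 × 200 = 1 to 0.05 × 200 = 10.

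The number actually randomised is not stated.

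**4. Effect on the OS hazard ratio.** Use the survival and accrual assumptions of step 2, a hazard ratio of 1.00 (CO-1686 vs erlotinib) in dosed patients, and a death rate k times higher in never-dosed patients. For arm a with never-dosed share p:

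- at risk: R_a(t) = [(1 − p)·exp(−λt) + p·exp(−kλt)]·G(t)
- deaths: D_a(t) = [(1 − p)·λ·exp(−λt) + p·kλ·exp(−kλt)]·G(t)
- G(t) = 1 up to 18 months, then falls linearly to 0 at 36 months.

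The large-sample Cox estimate solves ∫ {D_C − (D_C + D_E)·e^β·R_C / (e^β·R_C + R_E)} dt = 0, with HR = e^β. For short follow-up of never-dosed patients, their terms are set to zero after 1 or 3 months.

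| Never-dosed, CO-1686 vs erlotinib | k = 2, full follow-up | k = 3, full follow-up | k = 3, followed 1 month | k = 3, followed 3 months |
|---|---|---|---|---|
| equal (0.5% or 5% in both) | 1.000 | 1.000 | 1.000 | 1.000 |
| 1% vs 3% | 0.986 | 0.978 | 0.998 | 0.994 |
| 3% vs 1% | 1.015 | 1.022 | 1.002 | 1.006 |
| 0.5% vs 5% | 0.968 | 0.952 | 0.995 | 0.987 |
| 5% vs 0.5% | 1.033 | 1.051 | 1.005 | 1.013 |

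Varying the assumed median OS (18, 24 or 36 months) and analysis time (30, 36 or 48 months), the full-follow-up extreme with k = 3 runs from 0.940 to 0.962, or 1.039 to 1.063 reversed.

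**5. Which follow-up column applies?** The Synopsis (Study Design) and Sections 5.1.4 and 12.1 start survival follow-up when treatment is discontinued. Section 9.5 starts it after the End-of-Treatment Visit. A patient who never began treatment triggers none of these. Full follow-up of such patients is therefore not assured, and the full-follow-up columns are ceilings for their scenarios.

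**The case against.** The strongest reply is that little is at stake. The sponsor confirms eligibility before randomisation, the first dose must follow within 3 days, and both arms receive an active oral drug, so non-starters should be few. OS is secondary and has no stated power, and the Synopsis says that crossover may limit its use. Development has been discontinued, enrolment is closed, and Appendix D schedules no further survival status. All of this stands and is why the point is minor. It does not make first dose a sound origin. OS remains a listed secondary endpoint, a clinical study report is still required, and crossover was confined to Phase 2.

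A reader might infer that the plan breaks a promise to analyse OS by intention to treat. The documents do not support that. Section 11.1 ties the ITT population by name only to the Phase 3 primary efficacy analysis, and the OS paragraph names no population. The wording in Section 11.2.1 about randomised groups can be read as saying how groups are formed, not that every randomised patient must be included.

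A reader might also contrast OS with time to symptom worsening, which Section 11.2.4.2 counts from randomisation. That contrast is weak, because the quality-of-life baseline is defined relative to first dose, so an undosed patient lacks a clear baseline there too. ORR is likewise counted from the start of treatment. The sound comparison is with the two PFS endpoints, and these objections do not touch it.

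**Conclusion.** The point holds as a minor one. OS has the wrong origin for a randomised comparison and no named population. As written, a never-dosed patient counts for PFS and is lost from OS.

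The size rests on assumptions, because the documents give neither a never-dosed rate nor any sign of which arm would have more. Equal rates leave the hazard ratio at 1.00. The most unequal case examined moves it by about 0.05 in either direction (0.04 to 0.06 across the sensitivity settings), and only if never-dosed patients have full survival follow-up. With 1 to 3 months of follow-up the same case moves it by 0.005 to 0.013. It would be tempting to read the 0.05 as an expected bias favouring one drug. It is a ceiling for an assumed tenfold imbalance, and its direction is unknown. The primary invPFS analysis is unaffected.

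**What to change.** In the Overall Survival paragraph of Section 11.2.4.2, define OS as 1 plus the number of days from the date of randomisation to death from any cause, analysed in all randomised patients (ITT). Censor patients without a documented death on the date last known alive, or at randomisation if there is no later contact. A version timed from first dose can be kept as a sensitivity analysis.

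Report, by arm, how many randomised patients were never dosed and what survival data already exist for them. Under Appendix D participation ends after the End-of-Treatment visit, so this is a check of existing records.

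The cost is one definition, one censoring clause and one data check. The randomisation date is already needed for invPFS, and no new data collection is required.
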